#### **Physical and Laboratory Test Findings**

- p) Subjects must not be positive for hepatitis B surface antigen.
- q) Subjects who are positive for hepatitis C antibody if the presence of hepatitis C virus was also shown with polymerase chain reaction or recombinant immunoblot assay.

- r) Subjects with any of the following laboratory values
  - i) Hemoglobin < 8.5 g/dL
  - ii) WBC < 2000/mm^3 (< 3 x 10^9/L)
  - iii) Platelets < 100,000/mm^3 (< 3 x 10^9/L)
  - iv) Serum creatinine > 2 times the ULN
  - v) Serum ALT or AST > 2 times the ULN
- s) Any other laboratory test results that, in the opinion of the investigator, might place a subject at unacceptable risk for participation in the study.

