#### **Other Exclusion Criteria**

- x) Prisoners or subjects who are involuntarily incarcerated.
- y) Subjects who are compulsorily detained for treatment of either a psychiatric or physical (eg, infectious disease) illness.

Eligibility criteria for this study have been carefully considered to ensure the safety of the study subjects and to ensure that the results of the study can be used. It is imperative that subjects fully meet all eligibility criteria.

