#### Appendix 1 ACR Criteria

The diagnosis of Systemic Lupus Erythematosus requires the presence of four or more of the following eleven criteria, serially or simultaneously, during any period of observation.

1. Malar rash: fixed erythema, flat or raised, over the malar eminences, tending to spare the nasolabial folds
2. Discoid rash: erythematous, raised patches with adherent keratotic scaling and follicular plugging; possibly atrophic scarring in older lesions
3. Photosensitivity: skin rash as a result of unusual reaction to sunlight, as determined by patient history or physician observation
4. Oral ulcers: oral or nasopharyngeal ulceration, usually painless, observed by physician
5. Arthritis: nonerosive arthritis involving two or more peripheral joints, characterized by swelling, tenderness, or effusion
6. Serositis: pleuritis, by convincing history of pleuritic pain, rub heard by physician, or evidence of pleural effusion; or pericarditis documented by electrocardiography, rub heard by physician, or evidence of pericardial effusion
7. Renal disorder: persistent proteinuria, > 500 mg per 24 hours (0.5 g per day) or > 3+ if quantitation is not performed; or cellular casts (may be red blood cell, hemoglobin, granular, tubular, or mixed cellular casts)
8. Neurologic disorder: seizures or psychosis occurring in the absence of offending drugs or known metabolic derangement (e.g., uremia, ketoacidosis, electrolyte imbalance)
9. Hematologic disorder: hemolytic anemia with reticulocytosis; or leukopenia, < 4,000 per mm^3 (4.0 \_ 10^9 per L) on two or more occasions; or lymphopenia, < 1,500 per mm^3 (1.5 \_ 10^9 per L) on two or more occasions; or thrombocytopenia, < 100 \_ 10^3 per mm^3 (100 \_ 10^9 per L) in the absence of offending drugs
10. Immunologic disorder: antibody to double-stranded DNA antigen (anti-dsDNA) in abnormal titer; or presence of antibody to Sm nuclear antigen (anti-Sm); or positive finding of antiphospholipid antibody based on an abnormal serum level of IgG or IgM anticardiolipin antibodies, a positive test result for lupus anticoagulant using a standard method, or a false-positive serologic test for syphilis that is known to be positive for at least 6 months and is confirmed by negative *Treponema pallidum* immobilization or fluorescent treponemal antibody absorption test

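### The WBC and platelet exclusion limits in Section 4.2.1 each give two values that are not the same limit

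*Combined protocol and SAP*

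**What the plan says.** Section 4.2.1, under Physical and Laboratory Test Findings, excludes "Subjects with any of the following laboratory values". Item ii) is "WBC < 2000/mm 3 (< 3 x 10 9 /L" and item iii) is "Platelets < 100,000/mm 3 (< 3 x 10 9 /L", each with the second value in brackets. The bracketed value is identical on the two lines.

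The next item, s), is a discretionary clause: "Any other laboratory test results that, in the opinion of the investigator, might place a subject at unacceptable risk for participation in the study". The synopsis exclusion list has a similar investigator-opinion clause and no numeric white-cell or platelet limit. No other section restates these limits or says which unit takes precedence.

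The criteria are meant to be applied strictly. The closing paragraph of the eligibility section says "It is imperative that subjects fully meet all eligibility criteria", and Section 4.2 requires any exception to be approved before enrolment.

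**The concern.** An exclusion threshold has to be a single number. Here each line offers two, and the conversion between them is fixed, so they cannot both be the limit.

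These are hard safety gates for an immunomodulating biologic. The protocol itself lists serious or fatal infection among the drug's risks (Section 1.4). Low white-cell counts are also to be expected in this population: leukopenia is a classification criterion in both Appendix 1 and Appendix 2, and it is a scored item on the SLEDAI-2K sheet.

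If the limit is ambiguous, the two sites could apply different rules. A monitor could not say whether a given participant was correctly enrolled or a protocol violation.

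**Working it through.** **Inputs.** All come from the protocol: the two pairs in Section 4.2.1, exclusion r) ii and iii, and the paired values in the haematologic criterion of Appendix 1.

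**Formula.** One litre is 10⁶ mm³. A count per mm³ is therefore multiplied by 10⁶ and divided by 10⁹ to express it in 10⁹/L, which is division by 1000.

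**Check of the formula on the plan's own pairs.** The leukopenia criterion in Appendix 1 begins "leukopenia, < 4,000 per mm 3 (4.0" and continues with the per-litre unit.

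- Leukopenia: 4,000 / 1000 = 4.0, as printed.
- Lymphopenia: 1,500 / 1000 = 1.5, as printed.
- Thrombocytopenia: 100 × 10³ / 1000 = 100, as printed.

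The document therefore uses the ordinary conversion and gets it right elsewhere.

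**Applied to exclusion r).**

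| Line | Per mm³, as printed | Converted (10⁹/L) | Printed (10⁹/L) | Printed 10⁹/L value back-converted (per mm³) | Larger / smaller limit |
|---|---|---|---|---|---|
| WBC | 2000 | 2000 / 1000 = 2.0 | 3 | 3 × 1000 = 3000 | 3 / 2 = 1.5 |
| Platelets | 100,000 | 100,000 / 1000 = 100 | 3 | 3 × 1000 = 3000 | 100 / 3 = 33.3 |

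Neither printed pair can be reproduced.

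**Who is affected.**

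- WBC 2.0 to just under 3.0 × 10⁹/L (2000 to 2999/mm³): eligible on the per-mm³ figure, excluded on the per-litre figure.
- Platelets 3 to just under 100 × 10⁹/L (3,000 to 99,999/mm³): excluded on the per-mm³ figure, eligible on the per-litre figure.

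The errors run in opposite directions. The per-litre figure is the stricter one for white cells and far the looser one for platelets, so a rule of always using one unit does not give a consistently cautious result.

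**Can the intended value be inferred?** For platelets, yes. The classification criteria in Appendices 1 and 2 and the SLEDAI-2K sheet all put thrombocytopenia at 100,000, and the repeated 3 looks carried over from the line above. For white cells, no. The SLEDAI-2K sheet puts leukopenia below 3,000, so 3 × 10⁹/L is a natural cut-off, while 2000/mm³ is a natural lower limit that tolerates lupus leukopenia. On the 3 × 10⁹/L reading, every candidate whose screening count meets the SLEDAI-2K leukopenia threshold is excluded. On the 2000/mm³ reading, only those below 2000 are.

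**The case against.** The arithmetic is not in dispute. The case on the other side is about consequence.

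- **The platelet figure would mislead nobody.** A limit of 3 × 10⁹/L is clinically implausible, and a rheumatologist would use 100,000/mm³. This largely stands: the 33-fold gap measures a misprint and not a likely effect on enrolment.
- **Divergence by laboratory unit is an assumption.** There are two sites, and the protocol does not state what units their laboratories report. This stands as far as it goes. The conflict does not depend on it, however: anyone reading the white-cell line sees both values and has no rule for choosing.
- **There is a natural reading.** The per-mm³ figure comes first and the bracket looks like a gloss, or a cautious site could take the stricter value on each line. Both readings are reasonable, but they give different white-cell limits (2000 and 3000/mm³), and the text requires neither.
- **Other safeguards exist.** Investigators may exclude on any worrying laboratory result. Severe or uncontrolled haematologic disease is excluded, as is BILAG A outside the musculoskeletal system. Blood counts are repeated at each treatment visit, and Section 5.3.1 provides for dosing to be interrupted for toxicity. These make unsafe enrolment less likely, but they do not fix the number.
- **The text may have been damaged in reading.** Some unit strings in the appendices are garbled. The two lines in Section 4.2.1 show no such damage and carry the same clean bracket, so this is a reason to look at the source page and not a rebuttal.

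**Conclusion.** The concern holds. Both lines are wrong as written: the paired limits differ 1.5-fold for white cells and about 33-fold for platelets. The part that matters in practice is the white-cell range from 2.0 to just under 3.0 × 10⁹/L, where the same candidate is both eligible and excluded and the document cannot settle it. The platelet line is an evident slip that should be corrected at the same time.

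The conclusion rests only on unit conversion and on the absence of any governing rule. The sites' reporting units and the number of candidates in the conflict range are not given, so the number of participants who might be wrongly enrolled or wrongly excluded cannot be estimated. Neither the sample size nor the analysis of the primary endpoint is affected. The defect should be corrected because it sits in an operative safety criterion.

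**What to change.** Correct items ii) and iii) of exclusion r) in Section 4.2.1 so that each line states one limit in both units.

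- **Platelets:** below 100,000/mm³ (below 100 × 10⁹/L).
- **White cells:** either below 2000/mm³ (below 2 × 10⁹/L) or below 3000/mm³ (below 3 × 10⁹/L). The choice is clinical and belongs to the sponsor.

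The cost is a two-line correction to the protocol. If anyone has already been screened, the site should check whether any screening white-cell count fell between 2000 and 2999/mm³ and record which limit was applied.

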#### **Prohibited Treatments and/or Therapies**

- t) Subjects who have at any time received treatment with any investigational drug within 28 days (or less than 5 terminal half-lives of elimination) of the Day 1 dose.
- u) Any concomitant biologic DMARD, such as anakinra.
- v) Treatment with rituximab within the past 6 months (B cells must be detectable in peripheral blood at onset of treatment with study biologic); belimumab within the past 3 months, cyclophosphamide within the past 3 months prior to study baseline visit.
- w) Previous treatment with abatacept

Prednisone or equivalent at doses higher than 20 mg daily.

#### **Other Exclusion Criteria**

- x) Prisoners or subjects who are involuntarily incarcerated.
- y) Subjects who are compulsorily detained for treatment of either a psychiatric or physical (eg, infectious disease) illness.

Eligibility criteria for this study have been carefully considered to ensure the safety of the study subjects and to ensure that the results of the study can be used. It is imperative that subjects fully meet all eligibility criteria.

#### **4.2.2        *Women of Childbearing Potential***

Women of childbearing potential (WOCBP) include any female who has experienced menarche and who has not undergone successful surgical sterilization (hysterectomy, bilateral tubal ligation, or bilateral oophorectomy), and who is not postmenopausal. Post menopause is defined as:

- Amenorrhea ≥ 12 consecutive months without another cause, and a documented serum follicle stimulating hormone (FSH) level > 35 mIU/mL or
- Women with irregular menstrual periods and a documented serum follicle stimulating hormone (FSH) level > 35 mIU/mL or

NOTE: FSH level testing is not required for women  $\geq$  62 years old with amenorrhea of  $\geq$  1 year

Women who are using oral or other hormonal contraceptives, such as vaginal products, skin patches, or implanted or injectable products, or mechanical products, such as an intrauterine device or barrier methods (diaphragm, condoms, spermicides), to prevent pregnancy or who are practicing abstinence or who have a sterile (eg, vasectomy) partner should be considered to be of childbearing potential.

#### **4.2.3 Discontinuation of Subjects from Treatment**

If a study subject is found to have worsening disease activity during the duration of the study, the choice of using a rescue medication (e.g. increase prednisone dose but not to  $>20$  mg daily) will be considered. However, if significant worsening of disease activity is found at 8 weeks in comparison to baseline disease activity, the investigator will consider the discontinuation of the subject from the study after discussing in detail with the patient alternative SLE treatment strategies. Throughout the duration of the study, background allowed standard of care therapies (prednisone, MMF, leflunomide, hydroxychloroquine) will be continued at the baseline dosage.

Subjects MUST discontinue study treatment and withdraw from the study for any of the following reasons:

- Withdrawal of informed consent (subject's decision to withdraw for any reason)
- Any clinical adverse event (AE), laboratory abnormality, or intercurrent illness which, in the opinion of the investigator, indicates that continued participation in the study is not in the best interest of the subject
- Pregnancy
  - Instruct WOCBP to contact the investigator or study staff immediately if they suspect they might be pregnant (eg, missed or late menstrual period) at any time during study participation. Institutional policy and local regulations should determine the frequency of on-study pregnancy tests for WOCBP enrolled in the study.
  - The investigator must immediately notify BMS if a study subject becomes pregnant. The mechanism for reporting pregnancy is described in Section 7.6.
- Termination of the study by BMS
- Loss of ability to freely provide consent through imprisonment or involuntarily incarceration for treatment of either a psychiatric or physical (eg, infectious disease) illness

## **4.3 Concomitant Treatments**

### ***4.3.1 Prohibited and/or Restricted Treatments***

Initiation of therapy with any of the following medications or treatments during the study is not allowed:

- Methotrexate
- Azathioprine
- Cyclophosphamide
- Leflunomide
- Rituximab
- Belimumab
- Cyclosporine
- Tacrolimus
- Gammaglobulin
- Experimental therapies for treatment of SLE
- Plasmapheresis
- Prednisone or equivalent at doses >20 mg daily.

The prescribing label of all concomitant medications used as subject's background therapy should be evaluated by the investigator for continued administration during subject's participation in this study (e.g. known toxicities, drug-drug interactions).

Change in SLE standard of care (SOC) therapy after 12 weeks will not be permitted to allow assessment of efficacy of abatacept.

### ***4.3.2 Other Restrictions and Precautions***

Due to risk of infection, vaccination of subjects with any live vaccine is absolutely contraindicated for 3 months before and during the course of the study. In view of the long half-life of abatacept, study subjects should not receive a live virus vaccine for a minimum of 3 months following the last dose of abatacept.

## **4.4 Discontinuation of Subjects from Treatment**

Subjects MUST discontinue study treatment and withdraw from the study for any of the following reasons:

- Withdrawal of informed consent (subject's decision to withdraw for any reason)
- Any clinical adverse event (AE), laboratory abnormality, or intercurrent illness which, in the opinion of the investigator, indicates that continued participation in the study is not in the best interest of the subject

- Pregnancy
  - Instruct WOCBP to contact the investigator or study staff immediately if they suspect they might be pregnant (eg, missed or late menstrual period) at any time during study participation. Institutional policy and local regulations should determine the frequency of on-study pregnancy tests for WOCBP enrolled in the study.
  - The investigator must immediately notify BMS if a study subject becomes pregnant. The mechanism for reporting pregnancy is described in Section 7.6.
- Termination of the study by BMS
- Loss of ability to freely provide consent through imprisonment or involuntarily incarceration for treatment of either a psychiatric or physical (eg, infectious disease) illness

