## **2 STUDY OBJECTIVES**

### **2.1 Primary Objective**

Improvement of lupus inflammatory polyarthritis measured by proportion of patients who achieve >=20% improvement in tender and swollen 28 joint counts at 16 weeks.

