## **4            INVESTIGATIONAL PLAN**

### **4.1            Study Design and Duration**

This is a randomized placebo-controlled double-blind study for the 16 weeks, in patients with SLE whose active lupus manifestation is primarily arthritis. The study consists of a baseline visit, a 16-week treatment period (with visits every 4 weeks), and a telephone follow up 8 weeks after the last dose of study drug. Patients are expected to participate in the study for up to approximately 26 weeks (including screening visit).

Informed consent will be obtained at the Screening Visit, prior to patients undergoing any study procedures. Eligibility criteria will be assessed and medical history will be reviewed prior to Protocol Amendment 1, November 30, 2015

patient's participation in this study. Starting at the baseline visit, patients will receive 125 mg sc of abatacept or placebo every week for 16 weeks. Patients may continue on their stable background standard of care medications (according to the protocol) throughout the study. In the first dose visit, patients will be monitored for systemic symptoms for at least 1 hour after abatacept has been administered.

Subjects who discontinue the trial early, i.e. prior to Week 16 should come to a follow-up study completion visit within 1 week of treatment termination.

Unscheduled visits for safety or for any other reason may be conducted at any time during the study.

During the study period, at 4 week intervals, swollen and tender joint counts (28 joints), the British Isles Lupus Assessment Group (BILAG) score, SLE Disease Activity Index (SLEDAI 2K), Physician Global Assessment Score and Patient Global Assessment will be assessed in addition to routine safety laboratory and physical tests. Disease related immunology tests/biomarkers will be taken at baseline and 16 weeks.

Bilateral Posterior-Anterior (PA) Hand X-rays (including wrists) will be performed at baseline for all subjects. Ultrasound examination of the PIP (2-5), MCP (2-5), and wrist joints designated below will be performed at baseline and at 16 weeks. At baseline and 16 weeks, synovitis (18 joints), tenosynovitis and erosions will be assessed.

Please see Time and Events Schedule in Section 6.

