**5.3.1        *Dose Modifications for Adverse Events***

If there is evidence of toxicity, as determined by laboratory tests or by clinical assessment that could place the subject at increased risk in the judgment of the investigator, administration of abatacept should be interrupted and the investigator should notify BMS. Subjects may be considered eligible to continue with abatacept treatment only if full resolution of the adverse event is documented. If the adverse event completely resolves and the next dose of abatacept cannot be

administered within 14 days of the target date, then that scheduled dose should be skipped. The next dose of abatacept should then be administered on the next targeted day for administration.

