**Early Withdrawal/Termination Visit**

Early Withdrawal/Termination Visit will follow procedure as outlined for Visit 7 (week 24).

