***6.1.2 Study Drug Discontinuation***

If study drug administration is discontinued, the reason for discontinuation will be recorded.

Procedure	Screening	Baseline	Visit 2-3-4	Visit 5	Study follow up phone call at Week 24	Early Withdrawal/Termination Visit
Eligibility Assessments						
Phone call					X i	
Informed Consent	X					
Inclusion/Exclusion Criteria	X	X a				
Verify withdrawal criteria and safety stopping rules			X	X		X
Medical History	X					
Safety Assessments						
Physical Examination	X	X	X	X		X
Vital Signs	X		x	X		X
Height, weight						
Assessment of Signs and Symptoms		X e	x	X e		X e
Concomitant Medication review	X	X	X	X	X	X
Adverse Events Assessment		X	X	X	X	X
Review all Laboratory Assessments for safety		X	x	x		
Urine Pregnancy Test		X b	X b	X b		X b

Procedure	Screening	Baseline	Visit 2-3-4	Visit 5	Study follow up phone call at Week 24	Early Withdrawal/Termination Visit
Laboratory Assessments						
CBC & Platelets	X	X	X	X		X
Chemistry Panel	X	X	X	X		X
PPD or quantiferon gold	X					
Urinalysis	X	X	X	X		X
Hepatitis B surface antigen, hepatitis C virus antibody	X					
Lupus Biomarkers (cytokines))		X		X f		X f
Anti-dsDNA, C3, C4, IgG		X	X	X		X
ANA,anti-CCP, rheumatoid factor	X					
HIV testing	X					
β-HCG serum test	X b					
Biomarker Sample Collection		X		X		
Efficacy Assessments						

Procedure	Screening	Baseline	Visit 2-3-4	Visit 5	Study follow up phone call at Week 24	Early Withdrawal/Termination Visit
Physician Global Assessment		X	X	X		X
Patient Global Assessment		X	X	X		X
Joint x-ray		X c				
Joint ultrasound		X d		X d		X d
SLEDAI-2K	X	X	X	X		
BILAG 2004	X	X	X	X		
28 Tender/Swollen Joint Count	X	X	X	X		X
Clinical Drug Supplies						
Dispense Study Treatment		X	X h			

- a. Review all inclusion/exclusion criteria including compliance with allowed concomitant medications and assess subject's final eligibility.
- b. Required for women of childbearing potential (Serum pregnancy test must be performed at screening. Urine pregnancy test must be performed at all subsequent visits)
- c. Bilateral Posterior-Anterior (PA) hand x-rays (including wrists) should be performed for eligible subjects (unless already performed within 4 weeks prior to Baseline visit).

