### **8.2 Populations for Analyses**

The study analyses will be performed at the termination of the study; once the last visit of the last patients has been recorded. The analyses will be performed on the 64 SLE patients enrolled in the study based on the inclusion and exclusion criteria as stated above.

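### Patients who stop study drug for listed reasons, including adverse events and pregnancy, must also leave the study, so an avoidable part of the week-16 primary data is lost by rule

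*Combined protocol and SAP*

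**What the plan says.** The primary objective (Section 2.1) is the proportion of patients with at least 20% "improvement in tender and swollen 28 joint counts at 16 weeks".

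Sections 4.2.3 and 4.4 carry the same instruction: "Subjects MUST discontinue study treatment and withdraw from the study for any of the following reasons". The reasons are:
- withdrawal of consent;
- an adverse event, laboratory abnormality or intercurrent illness that in the investigator's opinion makes continued participation not in the patient's interest;
- pregnancy;
- termination by the company;
- loss of ability to consent through incarceration.

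For significant worsening at week 8, Section 4.2.3 is discretionary, but it again refers to the study and not only the drug: "the investigator will consider the discontinuation of the subject from the study after discussing in detail with the patient alternative SLE treatment strategies".

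Under Section 4.1, patients who leave before week 16 "should come to a follow-up study completion visit within 1 week of treatment termination". The schedule table marks "28 Tender/Swollen Joint Count" in the early-withdrawal column. The text on that visit says something else: "Early Withdrawal/Termination Visit will follow procedure as outlined for Visit 7 (week 24". The schedule has no Visit 7, and week 24 is a telephone call about adverse events.

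Section 8.2 states: "The analyses will be performed on the 64 SLE patients enrolled in the study". Section 8.4.3 plans multiple imputation for data missing at weeks 12 and 24 through loss to follow-up, with analyses run both with and without it.

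**The concern.** Stopping a drug and ceasing to be measured are separate events. When a protocol merges them, outcomes go missing that could have been observed, and they go missing for reasons that may depend on arm and prognosis. The protocol gives some ground for expecting an imbalance. In the earlier non-nephritis lupus trial it describes, serious adverse events occurred in 19.8% on abatacept and 6.8% on placebo, although it expects a lower rate over 16 weeks.

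At stake is whether the week-16 comparison of 64 patients rests on observed joint counts or, for some patients, on assumptions. With 32 per arm, one patient is worth about 3 percentage points of an arm's response rate (1/32 = 3.1%).

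**Working it through.** **1. Does any provision supply a week-16 outcome after a permanent stop for an adverse event or pregnancy?**
- Visits: Section 4.1 gives one visit within a week of stopping. Section 6.1.2 asks only that the reason for stopping be recorded. Section 7.6.2 requires discontinuation and follow-up procedures in pregnancy but does not name a week-16 joint count.
- Exit joint count: scheduled, but dated to the stop. It could serve as week 16 only for a stop so late that the visit falls within the 5-day window. No rule says how an earlier exit count enters the week-16 analysis.
- Treatment failure (Section 4.1 and the synopsis): triggered by prohibited therapy changes, or by prednisone above 10 mg at or after week 8. Neither covers an adverse-event or pregnancy stop as such.
- Imputation (Section 8.4.3): names weeks 12 and 24 and loss to follow-up. Week 16 is not named.

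So the outcome is neither collected nor assigned.

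**2. Reproduce the plan's figures (Section 8.1).**
Inputs: 67% vs 30%, alpha 0.05 (taken as two-sided), power 0.80. Pooled normal formula, mean proportion 0.485:

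n = [1.96 × √(2 × 0.485 × 0.515) + 0.842 × √(0.67 × 0.33 + 0.30 × 0.70)]² / 0.37² = 27.4, rounded up to 28 per group, as stated.

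Dropout: 35% / 3 = 11.7%, taken as 12%. Completers: 64 × 0.88 = 56.3, stated as 56, or 28 per arm. Missing: 64 − 56 = 8, or 4 per arm, from all causes.

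**3. Outer bounds on the difference in all 64 patients.**
Expected responders among 28 completers per arm: 28 × 0.67 = 18.76 and 28 × 0.30 = 8.40.

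| Assumption for the 4 missing per arm | Abatacept | Placebo | Difference |
|---|---|---|---|
| None respond on abatacept, all on placebo | 18.76/32 = 58.6% | 12.40/32 = 38.8% | 19.9 points |
| None respond in either arm | 18.76/32 = 58.6% | 8.40/32 = 26.3% | 32.4 points |
| All respond on abatacept, none on placebo | 22.76/32 = 71.1% | 8.40/32 = 26.3% | 44.9 points |

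Relative to the planned 37 points, that is −17 to +8.

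The synopsis instead expects 30 completers per arm, hence 2 missing. The same arithmetic gives (20.1 − 11.0)/32 = 28.4 points to (22.1 − 9.0)/32 = 40.9 points.

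**4. Could this change a conclusion?**
Take 19/28 vs 8/28 among completers as an assumed result: 39 points, Fisher p = 0.007. Filling in 4 missing per arm gives 19/32 vs 12/32 at one extreme (22 points, p = 0.13) and 23/32 vs 8/32 at the other (47 points, p = 0.0004). With all missing counted as non-responders, 19/32 vs 8/32 gives 34 points, p = 0.011. Only the adverse extreme loses significance.

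**5. Power.**
At 67% vs 30%, the planned Fisher's exact test has power 0.71 with 28 per arm and 0.82 with 32. The second figure is an upper bound: it needs every outcome recovered, with the recovered patients responding at the planned rates.

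**The case against.** The strongest reply is that the rule is narrower than it looks. It applies to listed reasons only. The adverse-event item turns on whether continued participation in the study is in the patient's interest, which is a judgement about the study and not only the drug. Interruption with resumption is dealt with separately in Section 5.3.1: "Subjects may be considered eligible to continue with abatacept treatment only if full resolution of the adverse event is documented". Worsening is not on the mandatory list, and patients whose therapy or prednisone breaks the limits are already treatment failures. Joint counts are taken every 4 weeks and at exit, imputation is planned, and the sample size already allows for 8 dropouts.

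Most of this stands and limits the point. A reader might infer three stronger things that the documents do not support:
- **That everyone who stops drug is removed and never assessed.** Interruptions may resume, and an exit joint count is scheduled.
- **That all 8 expected losses are created by this rule.** The 12% is all-cause, scaled from another trial. Withdrawn consent, loss to follow-up, incarceration and study termination lose data under any wording.
- **That the effect could move by 25 points.** That is the full width between two opposite extremes (44.9 − 19.9). The movement from 37 is −17 or +8, and each extreme requires every missing patient to respond in one arm and none in the other.

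The reply does not fill the gap for a permanent stop for an adverse event or pregnancy, or for a patient removed at week 8 for worsening before meeting a failure rule. Allowing for dropout in the sample size replaces numbers. It does not remove bias if the losses differ by arm.

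**Conclusion.** The point holds in this limited form. For permanent stops under the listed reasons before about week 16, the protocol removes the patient from the study, collects no week-16 joint count and assigns no primary outcome, while Section 8.2 counts that patient in the analysis.

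The number affected is not known. It lies between 0 and the 8 all-cause dropouts that Section 8.1 expects, and the documents give no breakdown by reason. The range of about 20 to 45 points is therefore an outer bound. It assumes that all 8 are missing, 4 per arm, and that completers respond at the planned 67% and 30%. The likely effect is smaller. The change is still worth making, because it is cheap and the missing week-16 counts cannot be obtained after the trial.

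**What to change.** Leave the treatment-stopping criteria unchanged and separate them from study withdrawal in Sections 4.1, 4.2.3 and 4.4:
- Patients who permanently stop study drug, still consent and are able to consent, and for whom the investigator does not judge continued visits to be against their interest, keep the remaining 4-weekly assessments, at minimum the week-16 joint count.
- Withdrawn consent, sponsor termination and loss of ability to consent still end participation.
- Name week 16 in the imputation plan of Section 8.4.3, and have it cover patients who leave under these rules as well as those lost to follow-up.
- Reconcile the early-withdrawal visit across Section 4.1, the visit text that refers to a Visit 7, and the schedule table.

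The visits already exist in the schedule. The cost is amended wording and modest retention effort for a few patients. The documents give no visit budget, so no monetary figure can be attached.
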